7.4.1 Safety Criteria for Adjustment or Stopping Doses

7.4.1.1 SEL-212 or Placebo

A patient will be withdrawn from study drug for meeting the following stopping rule:

- sUA level < 2.0 mg/dL, measured 1 hour after the infusion of the second component of study drug is completed during Treatment Period 1
- AND
- sUA level > 1.0 mg/dL measured at the Day 21 visit of Treatment Period 1 or sUA level > 6.0 mg/dL at the Day 21 visit of any of Treatment Periods 2-11

Stopping rules will be assessed by an independent, central, unblinded medical monitor.

If withdrawn from study drug during the double-blind treatment period (Treatment Period 1 to 6) or the double-blind extension period (Treatment Period 7 to 12), regardless of reason, the patient will continue study visits to the end of Treatment Period 12.

The window for all Day 21 visits is +2/-1 days. If a Day 21 visit sUA value drawn within the protocol window is not available, but if a sUA value drawn at an unscheduled visit after the Day 21 window is available prior to dosing that is ≤ 1.0 mg/dL during Treatment Period 1 or ≤ 6.0 mg/dL during Treatment Periods 2-11, the patient will not be required to be withdrawn from study drug and will be eligible to receive their subsequent dose.

If 1) a Day 21 visit sUA value drawn within the protocol window is not available and no subsequent sUA results are available or 2) a Day 21 visit sUA value drawn within the protocol window is not available and

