8.3.3 Enrolled Patient Withdrawal and Discontinuations

8.3.3.1 Withdrawal Procedures

Early termination from the study occurs when an enrolled patient withdraws consent or is lost to follow-up. The reason for withdrawal will be evaluated and recorded in the case report form (CRF) and source documents.

Patients may withdraw consent at any time. Reason(s) for withdrawal of consent, failure to return for the necessary visits, or termination from the study should be documented. All patients that withdraw

early upon termination should have the Early Termination visit assessments completed (i.e., End of Study assessments) ([Appendix A](#) or [Appendix C](#)), if the assessments pose no risk to the patient and the patient allows such assessments.

The Investigator should consult with the Sponsor/medical monitor prior to withdrawing study treatment from any patient in the study. Since this is a multiple-dose study, once dosed, patients generally should not be terminated by the Investigator. The patient should be followed through the end of Treatment Period 12, unless the patient withdraws consent or is lost to follow-up. In situations where continued participation in certain aspects of the study pose a risk to the patient, with consultation with the medical monitor, the Investigator should discontinue those procedures that pose a risk and should continue to collect data and conduct those assessments that do not put the patient at risk through the end of Treatment Period 12. Patients with compliance issues or major deviations that effect data quality will also continue to be followed through the end of Treatment Period 12 collecting as much data on the patient as possible, unless otherwise indicated by the Sponsor.

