9.3 Treatment Compliance

Study drug will be administered in the controlled environment of a clinical research center. Direct observation of the administration of the study drug by study staff will ensure compliance. The date and time of the start and stop of drug administration and volume infused will be recorded.

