During Screening, all patients should be tested for COVID-19 by an FDA Emergency Use Authorized COVID-19 molecular assay for detection of SARS-CoV-2 RNA. A patient with a positive test result is permitted to request re-testing. A patient who requests re-testing should wait at least 10 days after the date of the first positive COVID-19 diagnostic test, as long as no symptoms have developed. If the

second test is positive for COVID-19, then the patient will be excluded from enrollment. If the second test is negative for COVID-19, then the patient must be tested a third time at least 24 hours after the second test to confirm the negative result.

On Study:

Once a patient is enrolled in the study, the investigational site will manage the patient according to its institutional standards and procedures established for COVID-19. During the study, a patient presenting with both symptoms (only severe and critical illness as per definitions below) of COVID-19 and positive COVID-19 test results will be discontinued from study treatment. The patient will be permitted to resume study visits for continued assessments (but not treatment with SEL-212 or placebo) according to the institutional standards and/or procedures of the investigational site.

Patients with mild-moderate COVID-19 illness (as per definitions below) will be allowed to resume study visits (on treatment with SEL-212 or placebo) after resolution of acute symptoms of clinical disease (except for loss of smell and taste) and meeting quarantine requirements so long as their subsequent dose occurs ≤90 days from their prior dosing day as per section 7.4.1.1. Patients with mild-moderate COVID-19 illness can continue **non-dosing study visits** as per protocol mandated visit window prior to resolution of acute symptoms according to the institutional standards and/or procedures of the investigational site.

Enrolled patients in the study with mild-moderate COVID-19 illness can be treated with anti-SARS-CoV-2 monoclonal antibodies. These patients will be allowed to resume study visits (on treatment with SEL-212 or placebo) after 2 weeks of receiving monoclonal antibodies, and confirmation of resolution of acute symptoms of clinical disease (except for loss of smell and taste), and meeting quarantine requirements so long as their subsequent dose occurs ≤90 days from their prior dosing day as per section 7.4.1.1.

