3. Treatment Period 6 only. Treatment Period 6 Day 28 assessment will be used for Treatment Period 7 Day 0 pre-dose assessment. Do not repeat sample collection on Treatment Period 7 Day 0.
4. Premedication to minimize potential infusion reactions: oral antihistamines at 12 (± 2) hours and 2 (± 1) hours and IV steroids at 1 (± 0.5) hours prior to study drug.
5. Obtain sample prior to study drug infusion.
6. Obtain sample 1 hour (+15/-0 min) after completion of infusion of Component 2. If a patient is withdrawn from study drug, the post-dose uricase activity and post-dose sUA samples do not need to be collected.
7. Component 1 will be SEL-110.36 at 0.1 mg/kg for patients randomized to treatment with SEL-212A and SEL-110.36 at 0.15 mg/kg for patients randomized to SEL-212B or will be placebo for patients randomized to placebo.
8. Before starting infusion with Component 2, a period of up to approximately 30 minutes is permitted after completion of infusion of Component 1.
9. Component 2 will be SEL-037 for patients randomized to treatment with either SEL-212A or to SEL-212B or will be placebo for patients randomized to placebo.

PHASE 3 STUDY: SEL-212/301
VERSION: 6.1

EFFECTIVE DATE

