## **6.2. Estimands for Key Secondary Efficacy**

### **6.2.1. Estimands for 'Reduction of mean sUA as computed by subtracting the Baseline sUA level from the mean sUA during Treatment Period 6'**

The main estimand for the key secondary efficacy endpoint 'Reduction of mean sUA as computed by subtracting the Baseline sUA level from the mean sUA during Treatment Period 6' is defined as follows:

- Population: Of all patients with gout refractory to conventional treatment defined by the study inclusion / exclusion criteria, the analysis population will include patients who were randomized to study treatment and who were dosed (ITT population)
- Variable: Continuous variable showing the difference between the mean sUA value recorded in TP6 and the baseline sUA value for each individual.
- Population-level summary: Difference in LS means between each SEL-212 treatment group vs. placebo.
- Intercurrent events:
  - o All intercurrent events (as listed in 6.1 for the primary estimand) except deaths will be considered using the treatment policy strategy
  - o For deaths, the last available value will be used (while-on-treatment strategy), i.e. the baseline sUA value will be subtracted from mean sUA values across the most recently attended TP.

A second estimand for this key secondary endpoint will be defined similarly to the main estimand but with using the while-on-treatment strategy for all intercurrent events (as listed in 6.1 for the primary estimand).

The main and second estimands will be repeated three times, once with the population changed to the mITT, and the other with the population changed to the all randomized set, and thirdly with the population changed to the PP set.

This document is confidential.

**6.2.2.** Estimands for 'Percent reduction of mean sUA as computed by subtracting the Baseline sUA level from the mean sUA during Treatment Period 6'

The main estimand for the key secondary efficacy endpoint 'Percent reduction of mean sUA as computed by subtracting the Baseline sUA level from the mean sUA (area under the sUA time curve) during Treatment Period 6' is defined as follows:

- Population: Of all patients with gout refractory to conventional treatment defined by the study inclusion / exclusion criteria, the analysis population will include patients who were randomized to study treatment and who were dosed (ITT population)

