
This document is confidential.

assessments are available from Day 28 up to, and including Day 0, pre-treatment (0 h) in TP7) must be at least 80%.

For example, if a patient only has measurements on both Day 0 assessments and Day 8 (planned assessment for Day 7) then percentage of time with sUA level < 6 mg/dL for TP6 would be taken to be the percentage of time the sUA levels were < 6 mg/dL from Day 0 to Day 8. However, if the Day 7 planned assessment was taken on Day 6 then this patient would have a missing value for their response.

A frequency table of the percentage of responders in TP6 will be provided by treatment group in overall and stratified by tophus status at baseline for the ITT population. Additionally, a summary table with the total and percentage of time a patient has sUA values < 6 mg/dL in TP6 will be provided by treatment group in overall and stratified by tophus status at baseline for the ITT.

Summary table of the actual values and change from baseline for sUA results will be provided for each scheduled sampling time point – including extension phase - by treatment group. Additionally, mean sUA level, reduction in mean sUA and percent reduction in mean sUA from baseline during TP6 will be presented by treatment group.

- Mean sUA level is defined as the area under the sUA time curve (computed using the linear trapezoidal rule during Treatment period 6) divided by the corresponding time interval.
- Reduction in mean sUA is computed by subtracting baseline sUA level from mean sUA during Treatment period 6.
- Percent reduction in the mean sUA from baseline is computed as the mean sUA level during Treatment period 6 minus baseline sUA level divided by baseline sUA level multiplied by 100

The SUA levels will be visualized in a box-plot by assessment time and treatment.

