#### **9.3.2. Key Secondary Efficacy Analyses**

##### **9.3.2.1. *Reduction of mean sUA as computed by subtracting the Baseline sUA level from the mean sUA during Treatment Period 6***

Both estimands, as well as the estimands where the ITT is replaced by the mITT, all randomized and PP sets, for this key secondary efficacy will be tested between each SEL-212 treatment group versus placebo using an ANCOVA, with reduction of mean sUA at TP6 from baseline as the dependent variable and

This document is confidential.

treatment and randomization stratum as fixed effects, and baseline sUA value as covariates. Missing values of change from baseline will be multiple imputed by using the RPMM method considering tophus status at baseline and treatment group. The Least Square (LS) Mean difference between each SEL-212 and placebo treatments groups will be estimated along with its 97.5% confidence interval, and 2-sided p-values.

The change from baseline in mean sUA across TP6 will be summarized by treatment group on the ITT, mITT, all randomized and PP populations.

**9.3.2.2. *Percent reduction of mean sUA as computed by subtracting the Baseline sUA level from the mean sUA during Treatment Period 6***

Both estimands, as well as the estimands where the ITT is replaced by the mITT, all randomized and PP sets, for this key secondary efficacy will be tested between each SEL-212 treatment group versus placebo using an ANCOVA, with percentage change of mean sUA at TP6 from baseline as the dependent variable, treatment and, randomization stratum as fixed effects, and baseline sUA value as covariates. Missing values of % change from baseline will be multiple imputed by using the RPMM method considering tophus status at baseline and treatment group. The Least Square (LS) Mean difference between each SEL-212 and placebo treatments groups will be estimated along with its 97.5% confidence interval, and 2-sided p-values.

However, residuals from this model will be checked for conformity to normality assumptions. Differences from normality in these residuals will result in the dependent variable being log-transformed and the ANCOVA applied to this outcome, adjusting for the same covariates. This model will then be considered the primary analysis for this estimand.

The percentage change from baseline in mean sUA across TP6 will be summarized by treatment group on the ITT, mITT all randomized and PP populations.

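### Imputing missing Treatment Period 6 mean sUA from arm and tophus status alone overstates the treatment-policy effect if missing SEL-212 patients are off drug more often than observed ones

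*SAP*

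**What the plan says.** - **Imputation.** SAP 9.3.2.1: "Missing values of change from baseline will be multiple imputed by using the RPMM method considering tophus status at baseline and treatment group". SAP 9.3.2.2 uses the same two predictors for percent change. Neither section uses drug status, and baseline sUA enters only the ANCOVA.
- **Estimand.** SAP 6.2.1 and 6.2.2 say that all intercurrent events "except deaths will be considered using the treatment policy strategy". Off-drug TP6 values therefore belong to the target.
- **Follow-up off drug.** Under Protocol 7.4.1.1, after withdrawal from drug, "regardless of reason, the patient will continue study visits to the end of Treatment Period 12". Protocol Appendix B, footnote 6, waives only the post-dose samples: "If a patient is withdrawn from study drug, the post-dose uricase activity and post-dose sUA samples do not need to be collected".
- **Who leaves.** Protocol 8.3.3.1: "The patient should be followed through the end of Treatment Period 12, unless the patient withdraws consent or is lost to follow-up".
- **Dosing.** Infusions are given at the site, and Protocol 9.3 says: "Direct observation of the administration of the study drug by study staff will ensure compliance".
- **On-drug absences.** Under Protocol 12.1.8.7, patients with mild or moderate COVID-19 "will be allowed to resume study visits (on treatment with SEL-212 or placebo) after resolution of acute symptoms of clinical disease", so an on-drug patient can also miss TP6 samples.
- **Partial data.** SAP 9.1 defines mean sUA as the area under the curve "divided by the corresponding time interval", so an incomplete TP6 curve can still give a mean.

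**The concern.** The strongest known determinant of TP6 sUA in a SEL-212 arm is whether the patient was dosed in TP6. For anyone who left before TP6 the answer is known: no dose was given. The imputation ignores this. A leaver's donors are all observed patients of the same arm with the same tophus status, some of them still on drug, so the leaver is given on average the effect of the observed arm.

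At stake is the accuracy of the reported effect and its 97.5% interval for the first two key secondary endpoints in the hierarchy. The off-drug data that could correct it are collected by design.

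**Working it through.** **The plan's figure behind the 8%.** Protocol 13.1 and SAP 3.5 assume 45% against 5% response, two-sided alpha 2.5%, 90% power and a continuity-corrected chi-square test.
- Uncorrected: n = (2.2414 × √(2 × 0.25 × 0.75) + 1.2816 × √(0.45 × 0.55 + 0.05 × 0.95))² / 0.40² = 26.7.
- Corrected: (26.7/4) × (1 + √(1 + 4/(26.7 × 0.40)))² = 31.5, so 32 per arm.
- With about 8% early termination: 32/0.92 = 34.8, so 35 per arm.

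Both figures reproduce. The 8% is thus an allowance for early termination. Of 40 patients it is 3.2 per arm.

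**Bias formula.** Let d = share of a SEL-212 arm with missing TP6 mean sUA, p = share of the whole arm on drug in TP6, and s = share of the missing patients on drug. Take the off-drug effect as zero. The true arm effect is proportional to p. The observed patients, and hence the imputed ones, have on-drug share (p − s·d)/(1 − d). So:

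relative overstatement = (p − s·d) / (p·(1 − d)) − 1

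It is 0 when s = p and negative when s > p. With s = 0 it is d/(1 − d) for any p.

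**Results.** The documents give no on-drug share. I set p = 0.45, equal to the planned responder rate, as an assumption. The 9.4% comes from Protocol 7.6.3.2.2: 13 consent withdrawals plus 3 lost to follow-up, 16/170, over both arms of an open-label Phase 2 trial that was still ongoing.

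| d | s = 0 | s = 0.25 |
|---|---|---|
| 5% | 5.3% | 2.3% |
| 8% | 8.7% | 3.9% |
| 9.4% | 10.4% | 4.6% |

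- Example: d = 8%, s = 0.25 gives (0.45 − 0.02)/(0.45 × 0.92) − 1 = 0.430/0.414 − 1 = 3.9%.
- Near balance at d = 8%: s = 0.40 gives 0.418/0.414 − 1 = +1.0%; s = 0.50 gives 0.410/0.414 − 1 = −1.0%.

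**Simulation of predictive mean matching.** Assumed, not in the documents: baseline sUA 8.7 mg/dL (SD 1.3), on-drug TP6 mean sUA uniform on 0.1 to 2, off-drug and placebo change with mean 0 and SD 0.8. Settings: 40 per arm, 60% with tophi, 10 imputations, 5 donors, 1,500 trials. The SAP does not say whether the ANCOVA is pairwise or three-arm, so both are shown.

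| d = 8% | Bias, mg/dL (pairwise / three-arm) | Coverage of 97.5% interval |
|---|---|---|
| p = 0.45, s = 0 | −0.30 / −0.30 (8.8% / 8.5%) | 95.4% / 97.7% |
| p = 0.45, s = 0.25 | −0.13 / −0.13 (3.7%) | not shown |
| p = 0.70, s = 0 | −0.46 / −0.48 (8.7% / 9.0%) | 88.8% / 93.9% |

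If on-drug sUA is instead 2 to 6 mg/dL, the first bias becomes −0.18. With no drug effect and 9.4% missing (three-arm, 3,000 trials), the SAP model and one that adds drug status both reject in 1.9% of trials, against a nominal 2.5%. For percent reduction at d = 8%, s = 0, the bias is −3.5 points on −39.5. This holds for the untransformed ANCOVA only.

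**The case against.** **Mostly off drug is not enough.** A reader might infer that bias follows once most missing patients are off drug. It does not. At p = 0.45 the arm is itself 55% off drug; if 60% of the missing patients are off drug (s = 0.40), the overstatement is only 1.0%. What counts is the excess over observed patients. This stands.

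**Few patients are involved.** About three per arm would be missing at 8%. Remote draws, unscheduled samples and partial curves all limit missingness. The standard error of the difference under the simulation's assumptions is 0.64 to 0.67 mg/dL, so a bias of 0.30 is under half a standard error and 0.13 is about 0.2. Return to urate-lowering therapy, allowed 60 days after the last dose (Protocol 7.4.1.1), shrinks the bias further. This stands, and it limits the size.

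**A tipping point is already planned.** SAP 9.2 applies one to the second primary estimand, which is treatment policy except for death and rests on the same TP6 sUA curve. So robustness to off-drug leavers is examined in binary form. A reader might also infer that SF-36, tender joints and HAQ-DI are tested for departures from missing at random while these endpoints are not. The sensitivity analyses in SAP 9.3.2.3, 9.3.2.6 and 9.3.2.7 use the same two-predictor RPMM, so they are no such test. What remains is that nothing planned tests the assumption on the mean sUA scale.

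**The percent endpoint may change model.** SAP 9.3.2.2 makes a log-transformed ANCOVA primary if residuals depart from normality. An arm split between on-drug and off-drug patients makes that likely, and the percent figure above would then lapse.

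**Conclusion.** The concern holds in conditional form. The main analysis of both mean sUA endpoints leans toward SEL-212 if missing SEL-212 patients are off drug in TP6 more often than observed ones. That is the likelier direction, because patients who left before TP6 receive no TP6 dose, but on-drug absences can reduce or reverse it. At 8% missing, the plausible range is 0 to 8.7%. The upper end requires every missing patient to be off drug with no residual effect.

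Three stronger readings are not supported:
- **That about 10% is expected, or is a ceiling.** The 10.4% needs the same extreme assumptions plus a 9.4% rate borrowed from another trial. The bound d/(1 − d) also grows with d. The documents give no missing rate for TP6 sUA.
- **That a false positive is likely.** Type I error is not inflated, and a change in the testing sequence is unlikely.
- **That interval coverage is safe, or is poor.** It is near nominal in the simulation at 45% on drug and about 89% to 94% at 70%. The documents do not give that share.

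All mg/dL figures rest on assumed sUA levels and SDs. The change is worth making because it is cheap; confidence in the size is medium.

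**What to change.** For the main estimand in SAP 9.3.2.1 and 9.3.2.2:
1. In the SEL-212 arms, add study drug received in TP6 (yes/no) and baseline sUA to the RPMM model. Off-drug missing values then come from observed off-drug patients of the same arm, and on-drug absences from on-drug patients. Baseline sUA matches the imputation to the ANCOVA; it does not remove the bias by itself.
2. State a fallback in advance: pool off-drug patients of both SEL-212 arms if donors are too few.
3. Impute placebo values from all observed placebo patients without the drug-status term. The stopping rule requires an early post-infusion sUA below 2.0 mg/dL, which placebo patients are not expected to reach, so off-drug placebo donors may be few or absent.
4. Add a delta or tipping-point analysis for both endpoints that shifts imputed SEL-212 values upward.

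**Cost.** SAP wording and a little programming; the variables are already collected. At 8% missing, all off drug, the expected off-drug donors per arm of 40 are 22 − 3.2 = 18.8 if 45% are on drug, and 12 − 3.2 = 8.8 if 70% are. In the 70% case the simulated interval widens by about 3% (2.69 to 2.76 mg/dL pairwise, 2.99 to 3.09 three-arm). In the 45% case it does not widen.

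**Residual bias.** Leavers may differ from retained off-drug patients. In the 45%-on-drug simulation at 8% missing, if leavers' sUA is 1 mg/dL lower, the bias is +0.08 with the change against −0.22 without it; if 0.5 mg/dL higher, −0.04 against −0.34. If off-drug leavers truly keep effect e and the observed arm averages E, the errors per imputed patient are |e| and |E − e|. The change is therefore better unless leavers keep at least half of the observed-arm effect. The delta analysis covers leavers who do worse than the imputation assumes.

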13. STATISTICS

Details of the statistical methods outlined in the protocol for this study, including the hierarchical ordering of the secondary endpoints, will be documented in a Statistical Analysis Plan (SAP), which will be finalized prior to database lock. The SAP may add additional exploratory analyses; modifications to the planned analyses will be identified as such in the final SAP.

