The main estimand for the key secondary efficacy endpoint 'gout flare incidence in Treatment Period 1 to Treatment Period 6' and 'gout flare incidence in Treatment Period 1 to Treatment Period 3' considers as variable of interest 'Incidence of gout flare during the whole treatment period from start of treatment until end of month 6'. and 'incidence of gout flare during the first 3 months of treatment'. Gout flare incidence is defined as the total number of gout flares a patient experiences in respective time period divided by the length of observation of the patient in this time period. The handling of all intercurrent events except death will be according to the treatment-policy strategy. For deaths, the while-on-treatment strategy will be used. The population-level summary is the difference in the gout flare incidences between each SEL-212 treatment group versus placebo for the whole treatment period (start of treatment until end of month 6) and for the first 3 months of treatment. The analysis will be performed separately for the whole treatment (Treatment Period 1 to Treatment Period 6) and for the first 3 months (Treatment Period 1 to Treatment Period 3). whereby the confirmatory statistical comparison will be performed first for the whole treatment, then for the first 3 months.

Further estimands for the key secondary efficacy during the double-blind treatment phase will be defined in the SAP.

For the above defined estimands, the key secondary efficacy endpoints which are numbered 1, 2, 8 and 9 will be tested between each SEL-212 treatment group versus placebo using an ANCOVA, adjusting for treatment, randomization stratum and baseline value of the respective variable. The Least Square (LS) Mean difference between each SEL-212 and placebo treatments groups will be estimated along with its 97.5% confidence interval, and 2-sided p-values.

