- Variable: Continuous variable showing the percentage difference between the mean sUA value recorded in TP6 and the baseline sUA value for each individual, i.e. the  $(\text{mean TP6 sUA value} - \text{baseline sUA value}) \div \text{baseline sUA value} \times 100$ .
- Population-level summary: Difference in LS means between each SEL-212 treatment group vs. placebo.
- Intercurrent events:
  - o All intercurrent events (as listed in 6.1 for the primary estimand) except deaths will be considered using the treatment policy strategy
  - o For deaths, the last available value will be used (while-on-treatment strategy), i.e. the baseline sUA value will be subtracted from mean sUA values across the most recently attended TP  $\div \text{baseline sUA value} \times 100$ .

A second estimand for this key secondary endpoint will be defined similarly to the main estimand but with using the while-on-treatment strategy for all intercurrent events (as listed in 6.1 for the primary estimand).

The main and second estimands will be repeated three times, once with the population changed to the mITT, and the other with the population changed to the all randomized set, and thirdly with the population changed to the PP set.

**6.2.3.** Estimands for 'The change from Baseline to Day 28 of Treatment Period 6 in the physical summary score of the Short Form Health Survey (SF-36)'

The main estimand for the key secondary efficacy endpoint 'Change from Baseline to Day 28 of TP6 of the Physical Summary Score of the Short Form Health Survey (SF-36)' is defined as follows:

- Population: Of all patients with gout refractory to conventional treatment defined by the study inclusion / exclusion criteria, the analysis population will include patients who were randomized to study treatment and who were dosed (ITT population)
- Variable: Continuous variable showing the change from Baseline to 6 months after start of study treatment (D28 of Treatment Period 6).
- Population-level summary: Difference in LS means between each SEL-212 treatment group versus placebo in the change from baseline in summary score of SF-36 questionnaire.
- Intercurrent events:

This document is confidential.

- All intercurrent events (as listed in 6.1 for the primary estimand) except deaths will be considered using the treatment policy strategy
- For deaths, the last available value will be used (while-on-treatment strategy)

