### **9.3. Key Secondary Efficacy Estimands and Analyses**

#### **9.3.1. Hierarchical Testing Approach of Key Secondary Efficacy Estimands**

If the superiority of both(one) SEL-212 treatment group(s) against placebo for the main estimand of the primary efficacy is shown with a p-value  $\leq 0.025$ , the hierarchical testing approach will continue to the testing of the main estimands of the key secondary efficacy comparing pairwise both (one) SEL-212 treatments against placebo. Only the main estimands of the key secondary efficacy will be tested in the successive order as defined in Section 6.2. The test result of the  $n^{\text{th}}$  key secondary efficacy estimand will be considered as confirmatory, if the p-value of the two-sided test of the previous estimand resulted in a value less or equal 0.025.

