## **12. Deviation from Analyses Planned in Protocol**

The key secondary endpoints for gout flare will be analyzed by ANOVA instead of ANCOVA as specified in the protocol, as adjustment for baseline is not possible given gout flare incidence is not assessed at baseline.

This document is confidential.

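### SAP 9.3.2.2 orders a log transform of percent change in sUA if residuals look non-normal, but percent change is negative whenever sUA falls, so the fallback cannot be run

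*SAP*

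**What the plan says.** SAP 6.2.2 defines the variable for key secondary 2: "Continuous variable showing the percentage difference between the mean sUA value recorded in TP6 and the baseline sUA value for each individual", with the Treatment Period 6 (TP6) mean first and baseline subtracted from it. SAP 9.1 has the same sign: "Percent reduction in the mean sUA from baseline is computed as the mean sUA level during Treatment period 6 minus baseline sUA level", then divided by baseline and multiplied by 100. Protocol 13.4.2 gives the same formula. The population-level summary in SAP 6.2.2 is a difference in LS means of this variable.

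SAP 9.3.2.2 fits an ANCOVA to it and then checks the residuals. "Differences from normality in these residuals will result in the dependent variable being log-transformed and the ANCOVA applied to this outcome". The next sentence gives that model its status: "This model will then be considered the primary analysis for this estimand".

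Under SAP 9.3.1 each key secondary result is confirmatory only "if the p-value of the two-sided test of the previous estimand resulted in a value less or equal 0.025".

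Protocol 13.4.2 says that the endpoints "which are numbered 1, 2, 8 and 9 will be tested between each SEL-212 treatment group versus placebo using an ANCOVA", and mentions no transformation. Protocol 13 adds that "modifications to the planned analyses will be identified as such in the final SAP". SAP 12 has one entry: "The key secondary endpoints for gout flare will be analyzed by ANOVA instead of ANCOVA as specified in the protocol". SAP 2.2 places the analysis after unblinding.

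**The concern.** The rule takes the log of a signed quantity. Every patient whose sUA is unchanged or falls has a percent change of zero or less, which has no logarithm. The patients lost are the treatment successes, and most of them are in the active arms. The word reduction in the endpoint's name does not help, because the formula subtracts baseline from the TP6 mean. The predictive mean matching in SAP 9.3.2.2 does not help either: it fills in missing values from observed percent changes, which are themselves negative for patients who respond.

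Key secondary 2 must reach p ≤ 0.025 for a dose before endpoints 3 to 9 can be confirmatory for that dose. If the check fails, the team must either drop every patient whose sUA did not rise or invent a repair: a shift, a ratio, or a return to the raw ANCOVA. Residuals from a model that contains treatment need the treatment codes, so the repair would be chosen with treatment known. No normality test or threshold is named, so whether the switch has fired is itself a judgement.

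**Working it through.** **Planning figures.** The documents give no power for key secondary 2. The response rates used below come from the primary-endpoint sample size (SAP 3.5: 45% vs 5%, two-sided alpha 2.5%, power 90%, continuity-corrected chi-square). That calculation reproduces: 32 per arm, and 32 / 0.92 = 34.8, so 35 per arm and 105 in total. Adding 15 gives 120, or 40 per arm.

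**The transformation.** Percent change = (TP6 mean − baseline) / baseline × 100. Illustrative values in mg/dL:

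| Baseline → TP6 mean | Percent change | log(percent change) | log(−percent change) | log(TP6 / baseline) |
|---|---|---|---|---|
| 8.5 → 1 | −88.24 | undefined | 4.480 | −2.140 |
| 8.5 → 6 | −29.41 | undefined | 3.381 | −0.348 |
| 8.5 → 8.5 | 0 | undefined | undefined | 0 |
| 8.5 → 9 | +5.88 | 1.772 | undefined | 0.057 |

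Reversing the sign moves the failure to patients whose sUA is unchanged or rises. A log ratio is defined for all four, but neither document mentions one.

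**How many patients are lost.** Responders per arm at the planned rates: 0.45 × 40 = 18 on SEL-212 and 0.05 × 40 = 2 on placebo. Each has no log value if the TP6 mean is at or below baseline. Non-responders whose sUA also fell come on top.

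**Is a responder's mean below baseline?** A responder spends at least 80% of TP6 below 6 mg/dL. Take baseline at 7, the screening threshold in inclusion criterion 7 (an assumption, since that criterion applies at Screening). Even with the first 80% sitting at 6, the mean exceeds baseline only if the remaining 20% averages above (7 − 0.8 × 6) / 0.2 = 11 mg/dL.

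**Would the check fail?** The documents give no distribution for percent change, so this part rests on assumptions. The design makes failure plausible: patients who meet the stopping rule leave study drug but keep attending visits, and the treatment-policy strategy keeps them in this analysis. An active arm therefore mixes controlled and off-drug patients.

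Simulation: 60 scenarios × 400 trials, 40 per arm, ANCOVA with treatment, stratum and baseline, Shapiro-Wilk at 0.05. Assumed inputs:
- baseline mean 8.7 (SD 1.4) mg/dL;
- 45% responders on SEL-212, 0% or 5% on placebo;
- responders' mean (SD) TP6 sUA 0.3 (0.3), 0.8 (0.5), 1.5 (1.0), 2.5 (1.5) or 3.0 (1.5);
- non-responders scattered around baseline with SD 0.8, 1.2 or 1.8;
- 0% or 50% of SEL-212 non-responders partly lowered (uniform 3 to 8).

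Results:
- the check fails in 6% to 98% of trials for one dose vs placebo, and in 8% to 100% with all three arms in the model, most often when responders' sUA is very low and tightly clustered;
- values ≤ 0 make up 72% to 85% on SEL-212 and 49% to 53% on placebo, and over 99.8% of responders have no log value in every scenario;
- with only the loggable values, p ≤ 0.025 occurs in 0.5% to 5% of trials, against 89% to 100% for the untransformed ANCOVA.

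The loss depends on how non-responders drift. A second set of assumptions was baseline about 8.5 (SD 1.2, floored at 7), responders uniform 0.1 to 5, and other patients' mean change −0.5 to +0.5 with SD 0.7 to 1.5. There the log is undefined in 58% to 87% of SEL-212 and 28% to 78% of placebo patients, leaving about 20 to 63 of 120 usable.

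**The case against.** The strongest reply concerns harm. The SAP does not tell anyone to drop patients, and a competent team would not. Under the same 60 scenarios, with small floors on baseline and sUA, sensible repairs perform about as well as the raw ANCOVA: p ≤ 0.025 in 85% to 100% of trials for a log ratio and 87% to 100% for shifted logs, against 88% to 100% for the raw ANCOVA. The log ratio and raw ANCOVA gave the same decision in 89% to 100% of trials. This stands. The 0.5% to 5% figure describes what follows if software sets undefined logs to missing, not the likely end result, and it partly reflects the assumption that non-responders scatter around baseline.

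Three further points have some force. The count of 18 and 2 assumes each responder's TP6 mean is at or below baseline. SAP 7.2 takes baseline as the last value before dosing, with no 7 mg/dL floor, so a responder with a low baseline could show a rise; most would still be negative. The fallback is still an ANCOVA with the same covariates, so whether it belonged in SAP 12 is arguable, and the case does not depend on it. Finally, a stated log ratio with a named trigger would also remove the undefined log. It would, however, keep a model switch decided with treatment known, and a log-scale contrast is not the summary that SAP 6.2.2 states.

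None of these points makes the written rule executable.

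**Conclusion.** The concern holds. The undefined log follows from the documents' own formula and needs no assumption; the absence of any shift, ratio, test or threshold is plain on reading. The fault is conditional: if the residuals are accepted as normal, the untransformed ANCOVA stands. The primary endpoint and key secondary 1 are unaffected. How often the fallback would be triggered is uncertain, as the 6% to 98% range shows. The choice of repair would rarely alter the test decision under the scenarios examined, but those scenarios are assumed. What remains is a confirmatory test gating seven further endpoints for each dose, with a primary model that cannot be fitted to the intended population and would have to be replaced after unblinding. That needs correcting before the SAP is used.

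**What to change.** In SAP 9.3.2.2, delete the sentence ordering the log transform and the sentence making that model primary. Keep the ANCOVA on untransformed percent change, as in Protocol 13.4.2, as the only confirmatory analysis of key secondary 2. This also keeps the analysis aligned with the difference in LS means in SAP 6.2.2 and leaves nothing further to declare in SAP 12 on this point. A robust-variance or rank-based analysis can be added as a sensitivity analysis if the sponsor wants protection against non-normality, but the repair does not need it. The cost is two sentences of SAP text; the protocol, data collection and sample size do not change.
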